Our long term goal is to develop a phase III study in response to a specific NIH FOA using high content screening of leucocyte LC3 puncta scores, qRT-PCR transcription factor EB (TFEB) scores, and assays of total DNA methylation and galectin-3, to gauge the magnitude of metformin's effects on autophagy and cell senescence as markers of aging in adults with prediabetes. This study will provide preliminary data for such a proposal and will also fill a knowledge gap regarding the use of validated biomarkers in this field. It will also contribute significantly to the overall anti-aging literature. The primary objective of this proposal is to validate the autophagy experimental design in humans by using leucocyte LC3, TFEB, Galectin-3, and total methylation of DNA scores as markers of autophagy activity and cell senescence.

1.2. State the hypotheses to be tested.

AIM 1: Demonstrate that metformin therapy will increase cellular autophagy as an inverse correlate of aging as measured by increases in LC3 and TFEB scores.

Hypothesis 1: In addition to beneficial effects on glycemia, body weight, and body composition, metformin therapy exerts beneficial effects on surrogate measures of autophagy and aging.

Primary outcome: Increased levels of LC3 in leukocytes.

AIM 2: Demonstrate that metformin therapy will mitigate evidence of aging as measured by increased DNA methylation and decreased serum galectin 3 among adults with prediabetes.

Hypothesis 2: Metformin therapy exerts beneficial effects on DNA methylation as measures of aging

Primary outcome: Increased DNA methylation in leukocytes.

AIM 3: Monitor the beneficial metabolic effects of metformin in adults with prediabetes. Hypothesis 3: Metformin therapy will elicit the expected beneficial effects on glycemia, body weight, insulin resistance, and body composition demonstrated in previous studies.

Primary outcome: Decreased A1c.

2. Background

2.1. Describe the relevant prior experience and gaps in current knowledge.

Anti-aging medicine is a burgeoning field, and accumulating data implicates the cellular process of autophagy as the primary mechanism of normal aging and the diseases associated with aging. Autophagy is considered to be a process of "cellular recycling" and is known to affect a spectrum of health and disease states associated with aging, including inflammatory disorders, metabolic syndrome and type II diabetes, cardiovascular disease, cancer and neurodegeneration. The dynamics of autophagy are strictly controlled by autophagy-related genes as well as by one of the central regulators of metabolism AMPK, the target of metformin. Autophagy also affects stem cells and cellular senescence. When the process of autophagy fails, the result is a state of chronic inflammation and degenerative diseases in many systems.

PROTOCOL TITLE: A Double-Blind, Placebo-Controlled Trial of Anti-Aging, Pro-Autophagy Effects of Metformin in Adults with Prediabetes

2.2. Describe any relevant preliminary data.

Diabetes can be considered a disease of premature aging, and many of the salutary effects of metformin therapy in diabetes can be interpreted as slowing or reversing the aging process. For example, in Western societies, 44% of patients with type 2 diabetes die within 10 years of diagnosis [1], and the incidence of, and mortality from, cardiovascular disease are 2–3 times greater in patients with diabetes than in the general population [2]. In current practice, metformin is the consensus first-line therapy for type 2 diabetes not only for its potent anti-hyperglycemic effects, but also for its well-documented improvements in endothelial dysfunction, hemostasis, oxidative stress, insulin resistance, lipid profiles, and fat redistribution [3]. Metformin may also decrease adverse cardiovascular outcomes independent from its glucose-lowering activity, and it likely has anti-proliferative effects in cancer and may also exert a neuroprotective effect [4]. These apparent pleiotropic effects of metformin make it a prime candidate for investigation as an anti-aging therapy.

What is Autophagy? Autophagy is a key feature of aging cells and a ubiquitous process of cellular senescence in human tissues. It can be described as an irreversible arrest in cellular proliferation. Autophagy is a key cellular homeostatic [5,6] and metabolic process [7-12] that is the center of a rapidly evolving area of biomedical research with broad fundamental and medical significance [13-28]. Autophagy responds to growth factors and is also exquisitely sensitive to cellular energy and nutritional status (e.g.- amino acids, glucose, ATP, NAD⁺, Acetyl-CoA, and neutral lipid stores) through very specific regulatory systems [29-38]. Autophagy affects a spectrum of human health and disease states [13, 17, 21-28], including inflammatory and autoimmune disorders [19,21,39,40], metabolic conditions such as obesity and diabetes [11,12,41-43], cardiovascular problems [17,25] cancer [13,15,20,28,44,45] neurodegeneration [18,22,40,46], infectious processes [21], and age-related diseases [47-49].

Autophagy and Metabolism: Autophagy enables regulation of glucose metabolism, and its failure contributes to the Metabolic Syndrome, insulin resistance, and diabetes [12,41,42,60-63]. Drugs such as metformin may affect autophagy [64]. Additionally, autophagy has connections with adipogenesis and lipolysis [11], and the cardinal regulators of metabolism in mammalian cells are also key upstream regulators of autophagy [9-11].

Autophagy and Inflammation: Autophagy directly and indirectly governs (often suppressing) activation of major inflammatory pathways associated with the pathogenesis of many diseases [17,19,39,50-54, 66]. It also modulates other global inflammatory processes, such as interferon responses [39]. These responses are key to maintaining normal immune homeostasis: failure of autophagy can lead to chronic inflammatory conditions (i.e.- Crohn's Disease [57,66-70], cancer [23,28], infections (tuberculosis [21,58, 59, 71,72] or HIV and other viruses [73-76]), and autoimmunity [56,77-82].

Synergy Between Autophagy, Inflammation, and Metabolism: Autophagy and metabolic abnormalities such as obesity, diabetes, atherosclerosis, and inflammation are interrelated [83-86]. For example, cholesterol crystals [87], fatty acids [88, 89], obesity-linked lipotoxicity of ceramide [89], and amylin [91] are known inflammasome agonists and inducers of inflammation. Autophagy suppresses inflammasome activation [17,19,21,39, 50-55]. Autophagy also modulates lipid metabolism [9-11].

PROTOCOL TITLE: A Double-Blind, Placebo-Controlled Trial of Anti-Aging, Pro-Autophagy Effects of Metformin in Adults with Prediabetes

All of this is relevant for aging. Rapamycin's effects on aging have been observed for years [92-117], and Metformin's impact on aging implicates similar mechanisms, but with improved metabolic sequelae [93,118].

2.3. Provide the scientific or scholarly background for, rationale for, and significance of the research based on the existing literature and how will it add to existing knowledge.

[figure not shown]
Numerous studies have documented the benefits conferred by the glucose-lowering agent Metformin. In animal models, Metformin is shown to increase both lifespan and healthspan, and a clinical trial (NCT02432287) is currently ongoing to determine whether this effect translates to humans, as well as how the medication alters the adult human transcriptome. *In vitro* studies demonstrate Metformin's ability to mitigate aging- and disease-related inflammation, oxidative damage, and diminished autophagy. Additionally, there are numerous cohort, case-control and meta-analysis studies confirming metformin's reduction in cancer-related death via hypothesized activity in the relevant mTOR, HER2, miRNA and TGF-alpha pathways. As such, NIH has issued FOA PA-17-073 (<https://grants.nih.gov/grants/guide/pa-files/PA-17-073.html>) to solicit additional clinical studies that will evaluate Metformin's effects on aging and age-related conditions.

3. Study Design

3.1. Describe the study design (e.g., observational; randomized placebo-controlled clinical trial, etc.)

We will perform a randomized, quasi-double blind, placebo-controlled trial of metformin in adult patients with prediabetes. Inclusion criteria will comprise individuals aged 30-70 years (inclusive) with prediabetes (defined as an A1c of 5.7-6.4%) and a BMI between 27 and 40 kg/m² (inclusive). Exclusion criteria will include prior treatment with metformin or other diabetes medications, pregnancy, the presence of significant renal dysfunction (Serum Creatinine > 1.3 mg/dl for women, > 1.4 mg/dl for men), severe hepatic dysfunction (AST or ALT > 3 times the upper limit of normal), ongoing alcohol or substance abuse, inflammatory bowel disease, ongoing glucocorticoid therapy, or inability to render informed consent.

Figure 1: Anti-Aging, Pro-Autophagy Effects of Metformin in Adults with Prediabetes

PROTOCOL TITLE: A Double-Blind, Placebo-Controlled Trial of Anti-Aging, Pro-Autophagy Effects of Metformin in Adults with Prediabetes

As summarized in the accompanying **Figure 1**, all subjects will complete four study-related visits. All visits will occur within a 7-day window of the target date. At Visit 1, informed consent will be obtained, a brief medical history and physical examination will be performed, and a health-history questionnaire will be completed by the participant. Blood samples will also be obtained for eligibility criteria at this visit. Women of child-bearing age will receive a urine pregnancy test at Visit 1.

At Visit 2, randomization to placebo or active Metformin will occur. All subjects will receive standardized instruction about diet and exercise for the prevention of diabetes and will be provided with a pedometer. Participants will subsequently be instructed to attempt to walk at least 10,000 steps per day five days during each week for the 12-week duration of the study. A step diary will be provided for subjects to complete daily to collect their step data.

As shown in **Table 1**, the following data will be collected at visit two (Week 0), visit three (4 weeks), and visit four (12 weeks).

After randomization, all subjects will receive 90 days worth of study medication in the form of either Metformin or Placebo (i.e.- nearly identical Calcium carbonate

$[\text{CaCO}_3]$) as prepared and labelled by the UNM Hospital research pharmacist, [name]. Subjects will start on doses of Metformin 500 mg po BID, and then the dose will be titrated up to 1000 mg po q AM and 500 mg po q PM over the course of 1 month, as tolerated. Subjects assigned to receive CaCO_3 will receive 648 mg po BID, and then the dose will be titrated up to 1296 mg po q AM and 648 mg po q PM over the course of 1 month, as tolerated.

Study investigators will be blinded to treatment assignment, and the study randomization list will be maintained by [name]. It should be noted that because Metformin has a distinctive odor, it is not possible to fully blind this study. For the purposes of this pilot study, however, we will take advantage of the fact that the dosages and appearance of CaCO_3 tablets and metformin tablets are very similar, and because study investigators and data collectors will be blinded to treatment, we believe that the study design is adequately robust.

FDA Regulatory Considerations: Metformin has an excellent long-term safety record and is already FDA approved for utilization in prediabetes. As such, attainment of an FDA IND is not necessary for this study. CaCO_3 is being administered in a manner consistent with current guidelines: 1000 mg of elemental calcium are recommended per day for adults, and our dosage delivers 780 mg of elemental calcium daily

(<https://medlineplus.gov/magazine/issues/winter11/articles/winter11pg12.html>).

Table 1: Study Visit Summary		
Visit Number	Data Obtained	Blood Volume
1 (Screening)	Blood: A1c, Lyses, BUN, Cr, Fasting Glucose, AST, ALT. Urine Pregnancy. Anthropometrics: Height, Weight Other: Health History, Physical Exam, AUDIT Questionnaire	22 ml
2 (Week 0, Baseline)	Blood: A1c, Fasting BMP, Insulin, LC3, TFEB, Galectin-3, DNA Methylation. Anthropometrics: Height, Weight, Body Composition by BIA. Other: Health History, Physical Exam, Distribute Step Diary.	60 ml
3 (Week 4)	Blood: A1c, Fasting BMP, Insulin, LC3, TFEB, Galectin-3, DNA Methylation. Anthropometrics: Height, Weight. Other: Health History, Physical Exam, Step Diary, Pill Counts.	60 ml
4 (Week 12)	Blood: A1c, Fasting BMP, Insulin, LC3, TFEB, Galectin-3, DNA Methylation. Anthropometrics: Height, Weight, Body Composition by BIA. Other: Health History, Physical Exam, Step Diary, Pill Counts.	60 ml

PROTOCOL TITLE: A Double-Blind, Placebo-Controlled Trial of Anti-Aging, Pro-Autophagy Effects of Metformin in Adults with Prediabetes

Lifestyle Intervention: All study participants will be educated in the importance of lifestyle modification in a manner consistent with the Diabetes Prevention Program [122], and all subjects will be expected to follow these instructions throughout the course of the 12 week study period. Specifically, subjects will be asked to attempt to achieve a modest reduction in total calories (500-1000 kcal/d) each day [123], as is consistent with the recommendations of the American Diabetes Association [124]. We will also ask participants to approach the physical activity recommendations of the Diabetes Prevention Program by asking them to walk 10,000 steps per day at least five days per week [125]. This amount of exercise will approximate the 150 minutes of moderately strenuous exercise achieved by participants in the lifestyle intervention arm of the Diabetes Prevention Program.

Study Population:

We will recruit potential subjects with prediabetes from the Endocrinology Clinics, from the CTSC participant recruitment service, and from the UNM Prediabetes Cohort Registry. This latter registry is the result of a small CDC-sponsored study performed at UNM a few years ago that identified 104

subjects with prediabetes out of 218 at-risk subjects who were screened (HRRC # 11-422) [126]. These subjects agreed to be contacted in the event of future research involving prediabetes. We will also employ CTSC-sponsored social media to recruit for this study, if necessary. We do not anticipate much difficulty identifying subjects who are interested in participating in this study. We estimate that 50 adults at risk for diabetes will need to be screened to find 30 eligible subjects with prediabetes to enroll in this study.

Data Analysis: For continuous variables (i.e.- A1c, Body Mass Index, HOMA-IR index, Body Composition, LC3 Score, TFEB Score, Total DNA Methylation, and Galectin-3 concentrations), we will analyze the change from baseline (Week 0) at Week 12 using a two-tailed unpaired *t*-test. Repeated Measures Analysis of Variance will also be performed using the 0, 4, and 12 week data with study drug as the grouping factor and study variable as the repeated factor. We will assume a moderate correlation of 0.7 for laboratory values obtained within subjects over time, and we will again compare responses in the subjects who received metformin with those who received placebo. Descriptive statistics comparing baseline characteristics of the study participants will employ the two-tailed unpaired *t*-test for continuous variables, or the Chi-Square or Fisher Exact test for frequency data, as appropriate.

Table 2: Study Outcome Measures		
Study Variable	What It Measures	Metformin Effect
Aim 1: LC3	This test quantitates intracellular autophagosome formation; a marker of autophagy.	Increase
TFEB	This test quantitates via qRT-PCR, changes in gene expression levels of TFEB-regulated genes.	Increase
Aim 2: Total DNA Methylation	This test quantitates the amount of methylated DNA in a 60 ng sample of isolated DNA from PBMCs relative to a methylated control sample.	Increase
Galectin-3	A regulatory molecule acting at various stages along the continuum from acute to chronic inflammation and fibrogenesis.	Increase
Aim 3: A1c	Average glucose concentration over 90 days.	Decrease
BMI	Body mass normalized to height.	Decrease
HOMA-IR Index	Insulin sensitivity using fasting glucose & insulin.	Decrease

PROTOCOL TITLE: A Double-Blind, Placebo-Controlled Trial of Anti-Aging, Pro-Autophagy Effects of Metformin in Adults with Prediabetes

Sample Size Determination and Power: Primary outcome variables for this study are “increase in LC3 Score from baseline” for Aim 1, “increase in total DNA methylation” for Aim 2, and “decrease in A1c” from baseline for Aim 3. Secondary outcome variables (not powered) are TFEB score for Aim 1, Galectin-3 concentrations for Aim 2, and BMI and HOMA-IR index (using fasting glucose and insulin) for Aim 3. These outcome variables are summarized in **Table 2**. We will enroll 30 subjects into this study and assume a dropout rate of 20%, leaving 12 subjects per group for data analysis. Sensitivity analysis will also be performed with an “intention to treat” analysis using the last value carried forward for subjects who dropped out.

For Aim 1, with 12 subjects per group, a difference in change in LC3 Score from baseline of 8 ± 4 Dots Per Cell (DPC) for Metformin vs. 3 ± 4 DPC for Placebo can be detected in PBMCs using a two-tailed, unpaired *t-test* with $\alpha = 0.05$ and $\beta = 0.83$. Baseline LC3 score is assumed to be 2 ± 2 DPC and not different between groups. This hypothesized difference is typical of those observed in [name] previous *in vitro* studies.

LC3 is our primary outcome variable for Aim 1. During the process of autophagy, autophagosomes engulf cytoplasmic components and concomitantly, the cytosolic form of LC3 (LC3-I) is conjugated to phosphatidyl ethanolamine, resulting in the autophagosomal membrane-bound form (LC3-II). LC3-II is a widely used marker to monitor autophagosome formation by quantitation of the number of LC3-labeled puncta (autophagosomes, or “dots”) per cell detected by fluorescence microscopy. An increase in LC3 puncta formation denotes an increase in autophagic activity. The [name] Lab has employed this technique in many different cell types, including human monocyte-derived macrophage cells (MDMs). Here, MDMs from human subject donors will be cultured and adhered in full media in 96 well plates and then immunostained to detect endogenous LC3 using Anti-LC3 polyclonal antibody (MBL P036) and a secondary fluorescent antibody. Plates will then be imaged using a Cellomics HCS scanner. This device will automatically capture cell images while identifying and quantifying LC3 puncta according to pre-set parameters in the HCS Studio software. This approach eliminates the problems of user subjectivity inherent in conventional microscopy studies while generating sufficient data from many hundreds of cells for robust and reproducible studies.

For Aim 2, we will employ the Imprint Methylated DNA Quantification Kit (Sigma-Aldrich, St. Louis, MO). This kit quantitates the amount of methylated DNA in a 60 ng sample of isolated DNA from PBMCs relative to a methylated control sample. Gomes and colleagues described a study comparing the total DNA methylation of young (26.5 years) and older (70.8 years) healthy subjects. They found a pattern of relative DNA hypo-methylation among the older subjects: $18.2\pm1.6\%$ in the older subjects versus $21.9\pm3.0\%$ in the younger subjects [127]. With 12 subjects per group, we can detect a difference of this magnitude with $\alpha = 0.05$ and $\beta = 0.82$.

For Aim 3, with 12 subjects per group, a difference in change in A1c from baseline of $0.7\pm0.4\%$ for Metformin vs. $0.2\pm0.4\%$ for Placebo can be detected with using a two-tailed unpaired *t-test* with $\alpha = 0.05$ and $\beta = 0.83$. Baseline A1c is assumed to be $6.1\pm0.4\%$ and not different between groups.

Potential Challenges: If adherence to lifestyle modification is significantly different between groups, this could become an important confounder. If this occurs, we will perform a

PROTOCOL TITLE: A Double-Blind, Placebo-Controlled Trial of Anti-Aging, Pro-Autophagy Effects of Metformin in Adults with Prediabetes

Repeated Measures ANCOVA using “steps per day” and “change in body mass” as covariates.

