3.2. Describe blinding, if applicable

Study investigators will be blinded as to study assignment of those 30 individuals enrolled, and the study randomization list will be maintained by UNM Hospital Research Pharmacist [name]. Randomization list will be devised and maintained by [name].

4. Inclusion and Exclusion Criteria

4.1. Describe how individuals will be screened for eligibility.

Screening will occur at the UNM CTSC Clinical Research Unit.

Inclusion criteria will comprise individuals aged 30-70 years (inclusive) with prediabetes (defined as an A1c of 5.7-6.4%) and a BMI between 27 and 40 kg/m² (inclusive).

Exclusion criteria will include prior treatment with metformin or other diabetes medications, pregnancy, the presence of significant renal dysfunction (Serum Creatinine > 1.3 mg/dl for women, > 1.4 mg/dl for men), severe hepatic dysfunction (AST or ALT > 3 times the upper limit of normal), ongoing alcohol or substance abuse, inflammatory bowel disease, ongoing glucocorticoid therapy, or inability to render informed consent.

4.2. Describe the criteria that define who will be included or excluded in your final study sample.

Inclusion criteria will comprise individuals aged 30-70 years (inclusive) with prediabetes (defined as an A1c of 5.7-6.4%) and a BMI between 27 and 40 kg/m² (inclusive).

Exclusion criteria will include prior treatment with metformin or other diabetes medications, pregnancy, the presence of significant renal dysfunction (Serum Creatinine > 1.3 mg/dl for women, > 1.4 mg/dl for men), severe hepatic dysfunction (AST or ALT > 3 times the upper limit of normal), ongoing alcohol or substance abuse, inflammatory bowel disease, ongoing glucocorticoid therapy, or inability to render informed consent.

During the screening assessments, we will employ the AUDIT questionnaire to determine whether the participant's behaviors constitute alcohol abuse. The AUDIT questionnaire (attached) has been added to the “Supporting Documents” section of the proposal. A score of 13 or more in a female, or 15 or more in a male, will constitute an exclusionary criterion for the study.

For the purposes of excluding other drugs of abuse, we will simply ask the participant the following question: “Have you used heroin, cocaine, or methamphetamine, or misused other narcotic drugs, over the past 30 days?” A yes response will constitute an exclusionary criterion for the study.

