Potential Challenges: If adherence to lifestyle modification is significantly different between groups, this could become an important confounder. If this occurs, we will perform a Repeated Measures ANCOVA using “steps per day” and “change in body mass” as covariates.

14. Provisions to Monitor the Data to Ensure the Safety of Subjects

This section is required when research involves more than Minimal Risk to subjects. Describe:

14.1. The entity (e.g., DMC, DSMB) or individuals (e.g., medical monitor) who will perform data and safety monitoring. Describe whether they are independent of or affiliated with the sponsor or investigator. If a DMC or DSMB is planned, describe the composition of the committee or board. Generally, a DSMB or DMC should be composed of experts in all scientific disciplines needed to analyze and interpret the data (e.g., epidemiologists, biostatisticians, subject matter experts).

We will employ [name], MD, to act as an independent monitor in the capacity of our Data Safety and Monitoring Board. [name] is independent of this study and has no vested interest in its outcome. Treatment for diabetes in this study is consistent with current standard of care, and the risks of Metformin or CaCO₃ therapy are generally mild and well characterized. We will track all study-related adverse events and prepare a report for [name] review each year prior to protocol renewal for the HRRC. We will track patients who are unable to tolerate study medication for any reason, including gastrointestinal complaints. We will also track and report all SAEs, as is standard for all clinical trials.

PROTOCOL TITLE: A Double-Blind, Placebo-Controlled Trial of Anti-Aging, Pro-Autophagy Effects of Metformin in Adults with Prediabetes

14.2. The safety information that will be collected and monitored.

Serum creatinine.

14.3. The frequency or periodicity of review of data, such as specified points in time or after a specific number of participants have been enrolled.

Safety and efficacy data will be collected at 0, 4 and 12 weeks. DSM reports will be prepared for the DSMB annually at the time of HRRC protocol renewal.

14.4. The plans for review of scientific literature and data from other sources that may inform the safety or conduct of the study.

Literature review was performed by [name], DO, and [name] from [name] lab.

14.5. The procedures for analysis and interpretation of the safety data.

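### The primary comparisons use change scores without Week 0 as a covariate: valid, but adjustment is a cheap gain for some outcomes

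*Combined protocol and SAP*

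**What the plan says.** Section 3.1 (Data Analysis) states: "we will analyze the change from baseline (Week 0) at Week 12 using a two-tailed unpaired" t-test. A repeated-measures ANOVA on Weeks 0, 4 and 12 is added, with "study drug as the grouping factor and study variable as the repeated factor", and the same paragraph says "We will assume a moderate correlation of 0.7 for laboratory values obtained within subjects over time". The t-test reads as the lead analysis, because the ANOVA is introduced as an addition and the power statements for Aims 1 and 3 name the t-test.

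Table 1 lists these blood tests at Weeks 0, 4 and 12: "A1c, Fasting BMP, Insulin, LC3, TFEB, Galectin-3, DNA Methylation". The Week 0 value of each primary outcome is therefore available.

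The power paragraphs say "Baseline LC3 score is assumed to be 2 ± 2 DPC and not different between groups", and "Baseline A1c is assumed to be" 6.1 ± 0.4%, again with no difference between groups.

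The only covariate model is conditional on unequal lifestyle adherence. Under Potential Challenges (Sections 3.1 and 13.2) the plan says "we will perform a Repeated Measures ANCOVA using" steps per day and change in body mass. Both are measured after randomisation, and neither is the Week 0 outcome. Section 13.1 adds no further method.

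**The concern.** A change score fixes the slope of Week 12 on Week 0 at exactly 1. ANCOVA estimates that slope. When the true slope is well away from 1, in either direction, the change score carries avoidable variance. When it is close to 1, ANCOVA gains nothing and pays for the estimated slope. With 24 expected completers, a few power points matter, and the data needed are already being collected.

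Chance imbalance is the second consideration. The plan assumes equal baselines, but with 12 per arm the standard error of the LC3 baseline difference is 2 × √(2/12) = 0.82 DPC. If the slope were 1.80, which the plan's own inputs imply (see the check), an imbalance of that size would shift the change-score difference by (1.80 − 1) × 0.82 = 0.65 DPC, or 13% of the hypothesised 5 DPC. On average over randomisations this causes no bias. Adjustment removes it in the trial that is actually run, and specifying it in advance avoids a later choice made with the data in view.

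**Working it through.** **Inputs from the plan.** 12 analysed per arm, two-sided α 0.05. LC3: mean changes 8 and 3, SD of change 4, baseline SD 2. A1c: mean changes 0.7 and 0.2, SD of change 0.4, baseline SD 0.4. Within-subject correlation r = 0.7. Methylation: difference 21.9 − 18.2 = 3.7, with cross-sectional SDs of 1.6 and 3.0 and no SD of change.

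**The plan's own figure.** Standardised difference: 5/4 = 1.25 for LC3 and 0.5/0.4 = 1.25 for A1c. Noncentrality = 1.25/√(2/12) = 3.06. With df 22, power is 0.833, which matches the stated 0.83 (the plan labels it β).

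**ANCOVA.** Hold the SD of change at the plan's value and solve for the Week 12 SD, s:

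- SD_change² = SD_b² + s² − 2·r·SD_b·s
- slope = r·s/SD_b
- residual SD = s·√(1 − r²)
- SE = residual SD × √((2/12) × 1.05), where 1.05 = 1 + 1/(2·12 − 4) allows for chance imbalance; df 21

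*LC3 at r = 0.7:* s = 5.14, slope 1.80, residual SD 3.67 against 4. Noncentrality = 5/(3.67 × √0.175) = 3.26; power **0.874**.

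*A1c at r = 0.7, baseline SD 0.4:* s = 0.56, slope 0.98, residual SD 0.40, the same as the SD of change. Power **0.813**.

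*Worst case, slope exactly 1:* the residual SD equals the SD of change and power is 0.813 for either outcome.

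**Sensitivity, LC3** (change score 0.833 throughout):

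| r | 0.3 | 0.4 | 0.5 | 0.6 | 0.7 | 0.8 |
|---|---|---|---|---|---|---|
| ANCOVA power | 0.827 | 0.815 | 0.815 | 0.833 | 0.874 | 0.939 |

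**Sensitivity, A1c.** Section 4.1 admits people "with prediabetes (defined as an A1c of 5.7-6.4"%. Values confined to a range of width 0.7 have an SD of at most 0.35, and 0.7/√12 = 0.20 if uniform, so the assumed 0.4 may be too large. Week 0 is a fresh measurement after screening and may vary somewhat more. ANCOVA power, against 0.833 for the change score:

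| Baseline SD | r = 0.5 | r = 0.6 | r = 0.7 |
|---|---|---|---|
| 0.40 | 0.908 | 0.843 | 0.813 |
| 0.35 | 0.855 | 0.820 | 0.817 |
| 0.30 | 0.826 | 0.813 | 0.830 |
| 0.25 | 0.814 | 0.818 | 0.849 |
| 0.20 | 0.815 | 0.833 | 0.874 |

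**Methylation (assumed inputs).** If the SD is 3.0 at both visits, SD of change = 3.0 × √(2 − 2r). At r = 0.5 this is 3.00 and power goes from 0.823 to 0.901. At r = 0.7 it is 2.32 and power goes from 0.961 to 0.976. If instead 3.0 is read as the SD of change, with equal variances at the two visits and r = 0.7, power goes from 0.823 to 0.862.

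**Simulation.** With 40,000 trials per setting at r = 0.7, t-test then ANCOVA: LC3 0.835 and 0.875; A1c (baseline SD 0.4) 0.832 and 0.811. Type I error was 0.048 to 0.051 for both methods.

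**The case against.** The strongest reply is that nothing is broken. Outcome definition, test and power calculation agree, type I error is held, and this is a pilot. The gain is also far from uniform. At the plan's own inputs it is +4 points for LC3 and −2 for A1c, and the methylation figure rests on assumed SDs. In the A1c table, 8 of the 12 cells with baseline SD 0.20 to 0.35 lie slightly below 0.833, one ties and three gain. The LC3 gain depends on r = 0.7, which is a general assumption for laboratory values; the LC3 effect itself comes from in vitro work. Finally, the t-test is named in the power text of Sections 3.1, 5.3 and 13.2, so more than one sentence would have to change.

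All of this is correct, and it is why the point is minor. It does not remove the case for adjusting. The true slopes are unknown. The loss is bounded at about 2 points, while gains in the scenarios above reach 8 to 11 points (methylation 0.82 to 0.90; LC3 0.83 to 0.94 at r = 0.8). The extra edits are still wording.

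**Conclusion.** The point holds, as a minor improvement in efficiency. The planned t-test is valid and its stated power for LC3 and A1c is right. Adjusting for Week 0 at 12 per arm gives 0.87 against 0.83 for LC3 and 0.81 against 0.83 for A1c at the plan's inputs. For A1c the range is 0.81 to 0.91 over baseline SD 0.20 to 0.40 and r = 0.5 to 0.7. Methylation gains under every reading tried, but those readings are assumptions.

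The LC3 and A1c figures hold the SD of change at the plan's value and assume a linear relation with the same slope in both arms. The benefit should be described as dependent on the outcome, not as a general reduction in variance.

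**What to change.** In Section 3.1 (Data Analysis), state: *The primary analysis of each primary outcome is the Week 12 difference between arms from ANCOVA with the Week 0 value of that outcome as covariate; the unpaired t-test on change is supportive.* The outcomes need no redefinition, because ANCOVA of the change with Week 0 as covariate gives the identical arm difference.

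If a repeated-measures model is preferred, it should include Week 0 as a covariate or constrain the Week 0 means to be equal across arms. A plain unadjusted Week 12 comparison is not a substitute: at r = 0.7 its power would be 0.63 for LC3 and 0.55 for A1c (baseline SD 0.4).

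Two matching edits:

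- In Sections 3.1, 5.3 and 13.2, label the stated power as that of the supportive t-test, or restate it for ANCOVA.
- For the supportive ANOVA, name visit as the repeated factor, and say that the test of interest is the arm difference in change from Week 0 to Week 12, not the drug effect averaged over Weeks 0, 4 and 12.

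The cost is wording, one degree of freedom and at most about 2 power points. No new data are needed and the sample size can stay as it is.
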